1. SPECIFIC AIMS

Aim 1: Map the cellular and synaptic targets of cervical electrical stimulation (CES).

CES circuit interactions at both the spinal and supraspinal levels will be characterized using a common structure comprising an electrical or magnetic conditioning stimulus followed by a test stimulus delivered at a range of intensities, sites, and interstimulus intervals (ISI). This will shed insight into which circuits CES activates, and how CES circuits interact with circuits activated by other exogenous neural stimuli.

Hypothesis 1.1: Conditioning subthreshold CES will potentiate spinal motor neuron responses to test transcranial magnetic stimulation (TMS) pulses. Depending on the timing of the effect, this would support either the mechanism of heterosynaptic summation between segmental Ia input and descending corticospinal input¹, or sensory cortical facilitation of motor cortex excitability²⁻⁴.

Hypothesis 1.2: Conditioning CES will increase persistence (number of responses per 20 stimuli) of spinal motor neuron F-responses to retrograde stimulation over the median and/or ulnar nerve. This would indicate CES's potential to modulate motor neuron excitability at the spinal level.

Hypothesis 1.3: Conditioning CES will reduce amplitude of median (flexor carpi radialis) H-responses, indicating that CES traveling via sensory afferents homosynaptically depresses ensuing H-reflexes^{5,6}. This would demonstrate the potential for CES to reduce hyperactive muscle stretch responses (spasticity)⁵ via segmental afferent interactions.

Aim 2: Determine optimal CES and volitional movement combination parameters for acutely facilitating concurrent arm and hand movements.

Volitional limb movements depend on the same corticospinal and motor neuron circuits as those activated by TMS and F-waves. Since preliminary data shows that subthreshold CES facilitates TMS responses, CES may also be able to facilitate volitional limb movements. The experiments in Aim 2 will shed light on this clinically applicable question.

Hypothesis 2.1: Subthreshold CES will *facilitate* concurrent arm and hand muscle activation, further indicating CES's ability to positively modulate corticospinal and/or motor neuron excitability. This would establish an opportunity to directly translate this paradigm for clinical benefit by combining repetitive subthreshold CES with repetitive task-oriented physical exercise training in a subsequent study.

Hypothesis 2.2: High-intensity suprathreshold CES will transiently *inhibit* concurrent arm and hand muscle activation. If observed, this 'spinal silent period' would shed insight into mechanisms underlying the 'cortical silent period' noted when cortical TMS is delivered during volitional contraction^{7,8}.

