Temporally linked (paired) neuronal firing can lead to lasting effects on synaptic and neuronal excitability through Hebbian-like mechanisms such as long term potentiation and synaptic summation^{66–69}. These paired stimulation techniques include paired associative stimulation (PAS), transspinal-transcortical stimulation, spinal associative stimulation, spike timing-dependent plasticity, and others^{2,70–77}. In a demonstration of spike timing-dependent plasticity in the cervical cord, TMS over the hand motor cortex was paired with high-intensity electrical stimulation over the ulnar nerve at the wrist⁷⁰. When repetitive (0.1 Hz, 100 repetitions) paired pulses were timed so the anterograde TMS signal arrived at cervical motor neurons 1-2 ms before the retrograde ulnar nerve signal, both able-bodied volunteers and subjects with SCI demonstrated increased TMS-evoked potentials in hand muscles and improved hand dexterity for at least 30 minutes after the end of paired stimulation⁷⁰. This suggested that synapses between upper and lower motor neurons underwent Hebbian-like strengthening. Other studies have found more evidence for the highly timing-dependent nature of synaptic effects, both at cervical and lumbar levels^{74,76,77}.

The advantages of non-invasive cervical electrical stimulation (CES)

Our group recently developed a novel configuration of transcutaneous CES. Our technique draws on lessons learned from other forms of non-invasive spinal stimulation referenced above. We have already applied for and received FDA designation as non-significant risk, and we are conducting two other IRB-approved human pilot studies to establish basic CES mechanisms and safety. As presented in the preliminary data, CES (**Figure 1**) comfortably elicits action potentials over multiple spinal cord segments simultaneously in both arms. CES activates spinal motor neurons indirectly via nerve roots, targeting either afferent or efferent fibers depending on stimulus intensity. This afferent or efferent root-stimulation approach provides a flexible portal to access synapses between upper and lower motor neurons, even in contexts of damaged motor circuitry⁷⁸.

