responded at lower thresholds than the arm myotomes (**Fig 2B**). Additionally, muscles in both arms simultaneously and symmetrically respond to CES in non-disabled subjects (**Fig 2C**).

CES targets different circuits at different intensities

When single CES pulses are delivered at peri-threshold intensity, latencies to the APB muscle are up to 3-5 ms longer than when delivered at higher stimulation intensity (not shown). When two CES pulses are given 40 ms apart at low intensity, the second pulse amplitude is strongly reduced, whereas at higher intensity, there is little to no decrement (**Fig 3**). These findings indicate that the CES circuit pathway can be selected by titrating intensity: at low intensity, CES travels a longer route from afferent to efferent neurons via synapses susceptible to post-activation depression^{1,6}. At higher intensity, CES directly (non-synaptically) activates efferent fibers (**Fig 3D**).

Subthreshold CES acutely facilitates muscle responses to cortical stimulation

To test whether subthreshold CES (80-90% of motor threshold) could facilitate response to suprathreshold TMS (120% of motor threshold), CES was delivered either alone or paired such that the CES pulse arrived at cervical motor neurons 10 ms prior to TMS pulse arrival or 1.5-5.0 ms after TMS pulse arrival. Preliminary results show that subthreshold CES facilitates the response to TMS when the TMS pulse arrives first (**Fig 4**), with similar trends among non-disabled, SCI, and ALS subjects. Since TMS travels via the same corticospinal pathways that mediate volitional movement, the fact that subthreshold CES facilitates TMS suggests that it may also facilitate volitional movement. This is a finding with potential for direct clinical translation. Note, only three different interstimulus intervals (ISI) were tested in this experiment. A much wider range of intervals needs to be tested to better understand and optimize this phenomenon.

[figure not shown]

Figure 4. Subthreshold CES acutely facilitates TMS-evoked potentials. Suprathreshold (120%) TMS and subthreshold (80-90%) CES were given alone or in combination. Response amplitudes were normalized to the response to TMS alone. Subthreshold CES facilitated the response to TMS alone when the TMS pulse arrived prior to CES, but not when the timing was reversed. **Amp**, amplitude.

Rationale:

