- Interpretation: Depending on the timing of the observed effect, this would support either the mechanism of heterosynaptic summation between segmental Ia input and descending corticospinal input (facilitation expected to occur at ISI between 2-15 ms)¹, or sensory cortical facilitation of motor cortex excitability (facilitation expected to occur at ISI between 20-60 ms²⁻⁴). This would also set the basis for using subthreshold CES to facilitate spinal cord motor responses during physical training (see Aim 2).

CES-peripheral nerve interactions:

- Hypothesis 1.2: Conditioning CES will increase persistence of F-responses (per 20 stimuli) to retrograde stimulation over the median or ulnar nerve.
- Hypothesis 1.3: Conditioning CES will reduce amplitude of median (flexor carpi radialis) H-responses.
- Speculative hypothesis 1.2: Conditioning suprathreshold CES will block spinal motor neuron F-responses delivered up to 10 ms later.
- Methods: If obtainable, F-wave pulse intensity will be ~110% of the intensity that results in maximal compound motor action potential (CMAP). H-reflex pulse intensity will be calibrated for amplitude ~20-25% of maximal CMAP⁸¹. Conditioning CES pulse intensity will be set between 30-175% of motor threshold. For subthreshold conditioning CES, either single or “theta bursts” (3 pulses at 50 Hz)⁴⁸ will be delivered. All pulse combinations will be delivered at a rate of 0.1 Hz, in pseudorandom parameter order, until 8 (CES-H combinations) or 20 (CES-F combinations) responses per parameter have been recorded.
- Interpretation: Hypothesis 1.2 would indicate that CES positively modulates motor neuron excitability at the spinal level; Hypothesis 1.3 would indicate that CES traveling via sensory afferents homosynaptically depresses ensuing H-reflexes⁶. This would demonstrate the potential for CES to reduce hyperactive muscle stretch responses (spasticity) via segmental interactions^{5,6}; ; and speculative hypothesis 1.2 would demonstrate that high-intensity CES pulses traveling anterogradely via efferent nerve roots collide with retrogradely traveling F-waves.

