If high-intensity CES inhibits concurrent volitional activity as predicted by Hypothesis 2.2, this would be analogous to the 'cortical silent period' (CSP) noted when cortical TMS is delivered during volitional contraction^{7,8}. The early phase of CSP (the first 50-75 ms after onset of the cortical motor-evoked potential) is mediated by poorly understood spinal mechanisms⁷. Our observations of the onset and duration of a 'spinal silent period' (SSP) in response to CES would shed mechanistic light on this phenomenon.

Aim 2 Data analysis: Rather than peak-to-peak amplitude, the effects of CES on concurrent volitional muscle contraction will be measured using RMS. RMS in 25 ms bins over the 200 ms following each CES pulse will be normalized to the baseline RMS during the 100 ms prior to each pulse. Repeated-measure analysis of variance (ANOVA) with factors of subject group, volitional effort intensity, CES intensity, post-stimulus timebin, and muscle will be performed. Post hoc pairwise comparisons will be made using Tukey's method.

Aim 2 Timeline:

Each subject will undergo two testing sessions on separate days, with a minimum of 24 hours and a maximum of two weeks between visits. Per subject, Aim 2 participation would therefore take 2 to 15 days. 24 subjects will be enrolled, resulting in 48 total testing sessions. A very conservative projection of completing 1.5 testing sessions per week would result in a timeline of 32 weeks or 8 months for completing Aim 2, not including results processing/dissemination.

4. Possible RISKS and protective actions

For subjects with ALS, there is a risk of falling during transfers between different testing positions. To minimize this risk, a clinician will be at the participant's side at all times to assess comfort and provide manual assistance/stabilization as necessary.

The surface electromyography recording and stimulating electrodes and tape have adhesive backing. Therefore, minimal risks such as transient skin irritation at the sites of surface electrode application may occur. Areas with excessive hair will be shaved prior to adhesive application.

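### Hypothesis 2.2 reads EMG silence after high-intensity CES as a spinal silent period without addressing direct motor-axon activation, which the protocol itself describes and which could cause silence unaided

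*Combined protocol and SAP*

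**What the plan says.** Section 1 states Hypothesis 2.2 as "High-intensity suprathreshold CES will transiently *inhibit* concurrent arm and hand muscle activation" and adds "If observed, this 'spinal silent period' would shed insight into mechanisms underlying the 'cortical silent period". The Aim 2 interpretation in Section 3 repeats the analogy with the cortical silent period (CSP) and gives the reason for interest: "The early phase of CSP (the first 50-75 ms after onset of the cortical motor-evoked potential) is mediated by poorly understood spinal mechanisms". The onset and duration of silence after CES are expected to inform that phase.

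Three other places describe what strong CES does:

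- Section 2, on the advantages of CES, says it acts on nerve roots, "targeting either afferent or efferent fibers depending on stimulus intensity".
- The preliminary data, on circuits targeted at different intensities, say "At higher intensity, CES directly (non-synaptically) activates efferent fibers". The background on non-invasive spinal stimulation says much the same of high-intensity pulses over the cord in general.
- Section 3, CES-peripheral nerve interactions, explains a predicted loss of F-responses by saying that "high-intensity CES pulses traveling anterogradely via efferent nerve roots collide with retrogradely traveling F-waves".

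The Aim 1 peripheral-nerve experiments and Aim 2 use the same CES range, 30-175% of motor threshold. Aim 2 compares CES with sham, varies CES intensity, and varies effort (100%, 50%, 15-20% of maximum). Silence is timed from the end of the CES-evoked potential to the return of voluntary activity. The repeated-measures ANOVA is written for RMS in 25 ms bins, with factors of group, effort, CES intensity, time bin and muscle.

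**The concern.** If strong CES fires motor axons directly, the EMG can fall silent for reasons unrelated to inhibition in the cord. Voluntary impulses can be cancelled by collision in the axons. Units driven by one synchronous volley also restart their firing cycle together, which leaves a gap before the next discharge. The protocol uses collision to explain a lost response in Aim 1 but does not consider it, or reset, when it interprets lost EMG in Aim 2.

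Hypothesis 2.2 could therefore be met whether or not CES engages a spinal inhibitory mechanism, and its stated value is mechanistic. Subject group is an ANOVA factor, so the same ambiguity reaches any difference between ALS and non-disabled participants. Such a difference could come from different firing rates or a different share of axons excited.

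**Working it through.** The plan states no figure on this point, so there is none to reproduce. The check has two parts.

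**1. Do the planned comparisons separate the explanations?**

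- *Sham against CES.* Shows that CES causes the silence. Both explanations predict that.
- *CES intensity.* Direct efferent recruitment rises with intensity, so both explanations predict more silence at higher intensity.
- *Effort level.* Reset silence should shorten as firing rate rises with effort. Stronger voluntary drive could also overcome synaptic inhibition sooner (an assumption), so this is a partial check.
- *Tests not planned in Aim 2.* Peripheral nerve stimulation during contraction, and an F-wave, H-reflex or TMS test of excitability during the silence.
- *ANOVA.* No term relates silence to the size of the direct response.

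**2. How long could reset alone last?** The documents give no firing rates, firing variability or share of active units excited, so all three are assumptions. The model has 120 motor units and 8 sweeps, interspike coefficient of variation 0.15-0.25, a reset at the pulse and no inhibition. The outcome is the time until pooled discharge returns to 50% of baseline. As a plausibility check, the shortest mean interspike interval in each band is 1000 / highest rate.

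| Firing rates (Hz) | 1000 / highest rate (ms) | Time to 50% of baseline, 80-100% of units reset (ms) |
|---|---|---|
| 8-12 | 1000/12 = 83 | 57-71 |
| 8-15 | 1000/15 = 67 | 49-60 |
| 10-20 | 1000/20 = 50 | 37-45 |
| 15-30 | 1000/30 = 33 | 25-30 |

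Each result falls somewhat short of the shortest mean interval, as expected when intervals vary.

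The share reset is the decisive input. Units that are not reset keep firing, so with a share p reset the trough sits at about (1 - p) of baseline:

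- p = 1.0: 0%
- p = 0.8: 20%
- p = 0.6: 40%
- p = 0.5: 50%

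At p = 0.5 or less a 50% criterion registers little or no silence. At p = 0.6 repeated runs gave first recovery at anything from about 7 to 28 ms, because the trough lies close to the criterion.

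These are not the durations the trial would record. The protocol uses a criterion based on the baseline standard deviation and starts the clock at the end of the evoked potential; the model does neither.

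**The case against.** The strongest reply is that the protocol never draws the conclusion at issue. It speaks of inhibiting muscle activation, of an analogy and of insight, and says that the early CSP "is mediated by poorly understood spinal mechanisms". A reader might infer that it claims to demonstrate a spinal inhibitory circuit, or that it contradicts itself. The text supports neither reading.

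A reader might also infer that the CSP analogy must go because TMS does not excite motor axons directly. That does not follow. Motor neurons discharged together by a TMS volley may also restart their cycle, so reset is a candidate for the early CSP too, and finding it after CES could be informative.

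Three further points have weight. High intensity has no numeric cut-off, so mixed afferent and efferent activation is possible at suprathreshold levels. Effort and intensity are varied, and the preliminary data offer latency as a marker of route (up to 3-5 ms longer near threshold), so Aim 2 is not without internal checks. This is a pilot, and the protocol ranks Hypothesis 2.1 as the more consequential result.

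What survives is narrower. The protocol's own account of high-intensity CES supplies a second explanation for the silence, Aim 2 does not name it, and no planned analysis uses the available markers to weigh it.

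**Conclusion.** The point holds as an unaddressed competing explanation. Observing silence after high-intensity CES would not by itself distinguish spinal inhibition from the consequences of direct motor-axon activation, and the planned comparisons do not separate them.

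Reset alone could last roughly 25 to 70 ms if 80-100% of active units are reset, with lower firing rates giving the longer times. At 8-12 Hz that falls within the 50-75 ms the protocol gives for the spinal phase of the CSP; at 15-30 Hz it falls short. At 50% or fewer reset there would be little or none. It would be too strong to say that reset accounts for the whole spinal phase, or that any observed silence must be axonal. The documents give no recruitment share to support either statement.

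No hypothesis predicts a group difference in silence, so misreading one is a risk to guard against, not a conclusion the plan draws. The change is worth making because it costs little and alters what Hypothesis 2.2 can support.

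**What to change.** **Wording (recommended).** Under Hypothesis 2.2 in Section 1 and in the Aim 2 interpretation, state that silence after CES acting by the direct efferent route is not in itself evidence of spinal inhibition. Name collision and reset beside it. Limit the conclusion, including any ALS versus non-disabled difference, to CES interrupting voluntary EMG, unless the silence is shown to exceed what the direct response explains. The CSP analogy may stay once both explanations are named. Cost: a few sentences.

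**Analysis (recommended).** Add to the Aim 2 data analysis a within-participant analysis of silent-period duration against the amplitude and latency of the CES-evoked potential on the same sweep, and across effort levels. Silence that grows with the direct response and shortens with effort is what reset predicts. Inhibition driven by the same volley could scale in the same way, so the result can shift the balance between explanations but not settle it. Cost: analysis time; no new data.

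**Reference condition (optional).** Add 8 sweeps of median-nerve stimulation at the wrist during finger opposition, matched to the size of the CES-evoked potential in abductor pollicis brevis (APB) and interleaved with the CES sweeps. Compare durations within participant. At the protocol's minimum 10 s spacing this takes 8 x 10 = 80 s per session, plus calibration time, with equipment already listed. It covers APB only, and the contrast is conservative because silence after peripheral stimulation also has spinal components. A finding of no excess would therefore not rule out a spinal contribution.

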2. BRIEF REVIEW OF RESULTS AND CURRENT STATE OF KNOWLEDGE

Amyotrophic lateral sclerosis (ALS) is a spinal cord disease. Many of the most striking features of ALS – muscular atrophy, fasciculations, and findings of denervation on electromyography – demonstrate the consequences of damage to lower motor neurons within the spinal cord. The almost pathognomonic spasticity and hyperreflexia seen in atrophied limbs reflects degenerating corticospinal axons in the lateral spinal cord ("lateral sclerosis"). Remaining motor circuits are weak, uncoordinated, and spastic⁹. Therefore, ALS shares many key features with incomplete spinal cord injury (SCI). Thus, some of the therapies aimed at strengthening neural transmission in SCI may warrant testing in ALS as well.

A large body of evidence in brain and spinal cord injury suggests that activating spared nerve circuits augments circuit and physiological function¹⁰⁻¹⁴. Impressive gains have been made in the SCI field by applying electromagnetic stimulation, including transcranial magnetic stimulation (TMS), direct current stimulation (DCS), and invasive epidural electrical stimulation^{10,15-21}. However, drawbacks exist, such as the unfeasibility of combining TMS with active exercises, the inability to directly map the timing or circuitry of DCS effects, and the risks of invasive surgery for epidural stimulation, especially in the ALS population.

Noninvasive electrical spinal stimulation lacks these drawbacks. We have developed a novel method of noninvasive cervical electrical stimulation (CES). Our technique draws on lessons learned from other forms of noninvasive spinal stimulation, mostly focused on the lumbar cord^{5,22–26}. However, these studies need to be supplemented with experiments that further investigate CES circuit interactions, not only within the spinal cord, but also between the cord and other parts of the nervous system. This proposal will address gaps in mechanistic and therapeutic understanding in the field of noninvasive spinal cord stimulation, and will establish the rationale for applying our novel technique in individuals with ALS.

ALS has been neglected by the field of neural stimulation. To our knowledge, the small body of work using neural stimulation in ALS has centered on the brain [[or phrenic nerve]], not the spine, and most studies have performed diagnostic rather than therapeutic stimulation^{27–32}. A literature search revealed only seven primary studies of therapeutic repetitive TMS or transcranial DCS for ALS, the majority performed by the Di Lazzaro group in Italy, which have not shown a clear benefit in ALS progression^{33–39}. A search of “amyotrophic stimulation” on the clinicaltrials.gov database showed one study with unknown active status recruiting ALS patients for therapeutic DCS in Italy, two studies recruiting ALS patients for diagnostic TMS in France, and our own unfunded pilot study of TMS paired with electrical stimulation at the James J. Peters VA Medical Center (see Preliminary Data). Both of these searches were last conducted on 21 February 2017. Thus, except for our own ongoing unfunded pilot study, there are no active clinical studies anywhere in the world of spinal stimulation for ALS. Given the limited therapeutic options available for ALS, this technology warrants testing even though electromagnetic stimulation may not halt or reverse underlying processes that contribute to ALS pathology such as inflammation, axonal transport defects, and protein aggregation⁴⁰.

Significance

ALS incidence is up to twice as high in Veterans from all eras of active duty⁴¹. Therefore, ALS is a 100% VA Service-Connected condition, and the experiments proposed here strongly align with RR&D’s mission. Treatments are extremely limited, and there remains no cure. Individuals with ALS and their loved ones are generally eager to seek out new options – unfortunately, this is often exploited by unethical purveyors of ill-defined mixtures of stem cells or herbal remedies^{42–44}. Therefore, rational, ethical, IRB-approved research studies are desperately needed. This pilot study, focused on mechanisms, safety, and short-term biomarkers of efficacy, represents an essential – and original – first step toward subsequent evidence-based studies of combined CES-exercise programs that will aim to improve clinical function in individuals with ALS.

This proposal focuses on non-invasive electrical stimulation over the spinal cord. Below, we will detail the state of this field, highlighting the gaps in mechanistic understanding and therapeutic application toward ALS and other conditions. We will thereby establish the rationale for testing and applying our novel technique of non-invasive cervical electrical stimulation.

Non-invasive brain stimulation

Transcranial magnetic stimulation (TMS) uses a transient focal magnetic field to induce action potentials in the underlying brain. TMS over the motor cortex transduces action potentials to descending corticospinal fibers^{45,46}. Repetitive TMS (rTMS) at 1 Hz is generally inhibitory, whereas at 5 Hz or greater, rTMS is generally excitatory⁴⁷. Higher-frequency (usually 50 Hz) ‘theta burst’ TMS may induce longer-lasting effects that are either inhibitory or excitatory based on burst patterns^{46,48}. Seminal TMS mechanistic studies will serve as guides for some of the experiments in this proposal^{45,46,48–50}.

Direct current stimulation (DCS) delivers a low-power electric current that modulates neuronal excitability⁵¹. In distinction from TMS, DCS delivers exclusively *tonic*, *subthreshold* stimulation⁵². Various cranial and spinal DCS configurations have shown promising effects in neurological and psychiatric disorders, as well as enhancement of normal function^{15,20,53–62}. However, there is no technique to directly map how the low-energy current distributes within the body, or to determine how individual variations in injury characteristics affect that distribution⁶³. Furthermore, the continuous nature of DCS makes it difficult if not impossible to elucidate timing-dependent synaptic changes. Therefore, although DCS has therapeutic potential, its underlying mechanisms are quite likely to remain a black box.

Invasive spinal stimulation

Epidural electric stimulation through implanted lumbar electrodes delivers tonic, motor-subthreshold stimulation, usually targeted toward the locomotor central pattern generator. In rodent SCI models, epidural stimulation combined with physical training and monoaminergic drug stimulation has led to recovered ability to walk on previously paralyzed hindlimbs^{19,64,65}. This work has been translated into humans with chronic motor-complete spinal cord injury as high as the C7 level, resulting in regaining some volitional leg movement while stimulation is turned on^{10,17}. These incredibly encouraging results support the utility of subthreshold spinal stimulation to improve neural circuit function. However, stimulator implantation carries the risks of invasive surgery – these risks are significantly higher in the cervical than lumbar spine.

Non-invasive spinal stimulation

Multiple transcutaneous spinal stimulation approaches have been developed, largely targeted at thoracolumbar locomotor circuits. Tonic stimulation over the T11 level at 3 Hz induces coordinated walking movements in uninjured volunteers²³. Adding simultaneous stimulation at the C5 and L1 levels increases motion coordination and range²². High-intensity phasic stimulation over the C7-T1 or T10-L1 levels activates efferent fibers in ventral motor roots to elicit action potentials in arm or leg muscles, respectively^{24,25}.

Transcutaneous biphasic stimulation can also elicit action potentials through afferent fiber pathways⁶. Subthreshold transcutaneous stimulation over T11-T12 for 30 minutes at 50 Hz led to reduced leg spasticity and evidence for improved motor function in three subjects with motor-incomplete SCI⁵. This effect was most likely mediated by activation of afferent spinal roots and their segmental interneuronal connections. We plan to exploit subthreshold cervical transcutaneous stimulation targeted at similar afferent pathways.

Temporally linked (paired) neuronal firing can lead to lasting effects on synaptic and neuronal excitability through Hebbian-like mechanisms such as long term potentiation and synaptic summation^{66–69}. These paired stimulation techniques include paired associative stimulation (PAS), transspinal-transcortical stimulation, spinal associative stimulation, spike timing-dependent plasticity, and others^{2,70–77}. In a demonstration of spike timing-dependent plasticity in the cervical cord, TMS over the hand motor cortex was paired with high-intensity electrical stimulation over the ulnar nerve at the wrist⁷⁰. When repetitive (0.1 Hz, 100 repetitions) paired pulses were timed so the anterograde TMS signal arrived at cervical motor neurons 1-2 ms before the retrograde ulnar nerve signal, both able-bodied volunteers and subjects with SCI demonstrated increased TMS-evoked potentials in hand muscles and improved hand dexterity for at least 30 minutes after the end of paired stimulation⁷⁰. This suggested that synapses between upper and lower motor neurons underwent Hebbian-like strengthening. Other studies have found more evidence for the highly timing-dependent nature of synaptic effects, both at cervical and lumbar levels^{74,76,77}.

The advantages of non-invasive cervical electrical stimulation (CES)

Our group recently developed a novel configuration of transcutaneous CES. Our technique draws on lessons learned from other forms of non-invasive spinal stimulation referenced above. We have already applied for and received FDA designation as non-significant risk, and we are conducting two other IRB-approved human pilot studies to establish basic CES mechanisms and safety. As presented in the preliminary data, CES (**Figure 1**) comfortably elicits action potentials over multiple spinal cord segments simultaneously in both arms. CES activates spinal motor neurons indirectly via nerve roots, targeting either afferent or efferent fibers depending on stimulus intensity. This afferent or efferent root-stimulation approach provides a flexible portal to access synapses between upper and lower motor neurons, even in contexts of damaged motor circuitry⁷⁸.

While we are excited to test CES paired with either peripheral nerve stimulation or TMS, TMS requires bulky, expensive equipment that makes it highly impractical to use in conjunction with concurrent physical exercise. In this proposal, we will take a more in-depth mechanistic approach to the CES technique itself, with the goal of establishing a single-modality stimulation paradigm that mediates beneficial synaptic plasticity in conjunction with physical exercise.

We emphasize that CES is inherently different from popularly used types of non-invasive electrical stimulation such as direct current stimulation (DCS, described above) and functional electrical stimulation (FES). FES targets peripheral nerves with suprathreshold pulses designed to directly stimulate motor units within one or more large muscles at a time. Separate FES electrodes are required for each targeted nerve/muscle. Critically, FES engages motor units in non-physiological order, from largest to smallest – this causes excessive muscle fatigue⁷⁹. In contrast, CES targets multiple root levels and both sides simultaneously, with the goal of using subthreshold intensity to amplify endogenous volitional neural circuit signaling.

[figure not shown]

Figure 1. CES schematic. Biphasic electrical pulses are delivered noninvasively over the cervical spine. The cathode is placed posteriorly over T1-T3 levels, and the anode is placed anteriorly over C4-C5 levels. Ground electrodes are placed over the distal clavicles. Depicted schematically on left, photographically on right.

Gaps in mechanistic understanding of spinal stimulation

As opposed to stimulation configuration and pairing with other modalities, the effect of timing between successive spinal cord stimuli has received less attention in comparison to similar experiments in the field of TMS. Extensive studies have defined rTMS effects over a range of pulse frequencies and patterns, in a broad variety of injury and disease contexts. A similarly rigorous definition of spinal stimulation timing effects has not yet been achieved. One reproducible finding has shown that at low suprathreshold intensities, a conditioning spinal pulse inhibits a second spinal pulse given 20-50 ms later^{1,5,6,80}. These findings, which we have confirmed in our own studies, indicate that at these intensities, spinal stimulation triggers afferent sensory fibers that activate motor neurons via synapses that are subject to homosynaptic depression. However, these studies need to be supplemented with experiments that more deeply investigate basic mechanisms of circuit interactions. In the TMS field for example, conditioning pulses inhibit test pulses given either 1-3 or 100-200 ms later, and facilitate test pulses given 8-15 ms later. The effects of these time intervals have revealed important brain circuit interactions termed short-interval cortical inhibition (SICI), long-interval cortical inhibition (LICI), and intracortical facilitation (ICF), respectively^{46,50}. Using conditioning and test stimuli over a broad range of time intervals, site, and modality combinations, we now expect to define similar types of circuit interactions mediating the response to CES.

Our team is optimally positioned to address these gaps – we already conduct studies involving electrical and magnetic stimulation in a well-run clinical research center; and we have already obtained FDA and IRB clearance to conduct human studies using our novel CES technique.

PRELIMINARY DATA

This preliminary data derives from an ongoing study investigating basic parameters of CES and its interaction with TMS. That study does not involve volitional movement, and lacks many of the basic mechanistic experiments proposed in the current application.

Noninvasive, non-noxious cervical electrical stimulation (CES)

We have designed a surface electrode configuration that effectively stimulates motor responses from multiple cervical levels simultaneously at non-noxious current outputs. One 5x10 cm cathode is placed longitudinally over

[figure not shown]
[figure not shown]
[figure not shown]

